**3. By antibiotic resistance:**

- Patients with antibiotic-resistant infections (based on antimicrobial susceptibility testing results of the admission specimen)
- Patients with antibiotic-susceptible infections (based on antimicrobial susceptibility testing of initial specimen)

**4. By admission severity:**

- Subgroup based on severity at enrolment, using either:
  - Based on NEWS score: Aggregate NEWS score 5–6 (medium clinical risk and  $\geq 7$  (high clinical risk)
  - Based on SOFA score: **0-5**: Low risk, mild organ dysfunction, **6-9**: Moderate risk, moderate organ dysfunction,  **$\geq 10$** : High risk, severe organ dysfunction.

**5. By presence of co-morbidities:**

- Participants with co-morbidities such as Diabetes Mellitus (DM), Chronic Kidney Diseases and other chronic diseases)
- Participants without co-morbidities

Data will be represented as summarised in **Table 2**.

We will summarise LOT, DOT, DDD using mean (SD) or median IQR depending on the distribution. If it is skewed the range may also be reported in addition to the IQR.

**Table 2. Summary of length of antibiotic therapy, length of hospital stay, number of mortalities, pattern of major organ dysfunction, and recurrent infections**

Characteristics	Procalcitonin (N=XX)	Control (N=XX)	Total (N=XX)	P value
Length of antibiotic therapy (LOT) days, median (IQR)	XX (XX-XX)	XX (XX-XX)	XX (XX-XX)	X.XXX
days, mean (95% CI)	XX (XX-XX)	XX (XX-XX)	XX (XX-XX)	X.XXX
Day of therapy (DOT) days, median (IQR)	XX (XX-XX)	XX (XX-XX)	XX (XX-XX)	X.XXX
days, mean (95% CI)	XX (XX-XX)	XX (XX-XX)	XX (XX-XX)	X.XXX
Defined Daily Dose (DDD) days, median (IQR)	XX (XX-XX)	XX (XX-XX)	XX (XX-XX)	X.XXX
days, mean (95% CI)	XX (XX-XX)	XX (XX-XX)	XX (XX-XX)	X.XXX

**STATISTICAL ANALYSIS PLAN**

Length of hospital stay days, median (IQR)	XX (XX-XX)	XX (XX-XX)	XX (XX-XX)	X.XXX
days, mean (95% CI)	XX (XX-XX)	XX (XX-XX)	XX (XX-XX)	X.XXX
Mortality, n (%)	XX (XX)	XX (XX)	XX (XX)	X.XXX
Pattern of major organ dysfunction, n (%)				
Convulsions	XX (XX)	XX (XX)	XX (XX)	X.XXX
Pulmonary oedema (Clinical)	XX (XX)	XX (XX)	XX (XX)	X.XXX
ICU admission	XX (XX)	XX (XX)	XX (XX)	X.XXX
ICU referral	XX (XX)	XX (XX)	XX (XX)	X.XXX
Invasive mechanical ventilation	XX (XX)	XX (XX)	XX (XX)	X.XXX
Non-invasive ventilation or high Flow nasal oxygenation	XX (XX)	XX (XX)	XX (XX)	X.XXX
Shock	XX (XX)	XX (XX)	XX (XX)	X.XXX
Inotrope/vasopressors	XX (XX)	XX (XX)	XX (XX)	X.XXX
Cardiovascular dysfunctions	XX (XX)	XX (XX)	XX (XX)	X.XXX
Fluid bolus required	XX (XX)	XX (XX)	XX (XX)	X.XXX
Spontaneous bleeding	XX (XX)	XX (XX)	XX (XX)	X.XXX
Blood transfusion	XX (XX)	XX (XX)	XX (XX)	X.XXX
Renal failure	XX (XX)	XX (XX)	XX (XX)	X.XXX
Haemodialysis / Peritoneal dialysis	XX (XX)	XX (XX)	XX (XX)	X.XXX
Recurrent infection confirmed or suspected after de-escalation of antibiotic	XX (XX)	XX (XX)	XX (XX)	X.XXX
XXX	XX (XX)	XX (XX)	XX (XX)	X.XXX

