### 2.1.3 Secondary objectives and endpoints

- To assess if procalcitonin guided de-escalation reduces antibiotic **consumption** and days of therapy with antibiotics.

- Consumption of antibiotics expressed as the Defined Daily Dosage (DDD)

*Definition of DDD: The basic definition for a defined daily dose is the assumed average maintenance dose per day for a drug used in its main indication in adults. Antibiotic use using the WHO DDD definition ([https://www.whocc.no/atc\\_ddd\\_index/](https://www.whocc.no/atc_ddd_index/)) will be determined for the most frequently prescribed Drugs in Bangladesh*

- Days of therapy with antibiotics (DOT)

Definition of DOT: One DOT represents the administration of a single antibiotic on a given day regardless of the number of doses administered or dosage strength. If a patient receives more than one antibiotic it will be added on with DOT of the first antibiotic. (Dalton et al. 2015)

- Number of days of parenteral antibiotic during hospitalisation period
- Number of days of antibiotic treatment during the hospitalisation period.

- To assess the safety of procalcitonin guided de-escalation of treatment
  - Overall mortality, mortality-associated with recurrent infection, and non-lethal recurrent infections.
- To assess the effect of procalcitonin guided de-escalation on length of hospital stay
  - Duration of hospital stay (ICU/ general ward)
- To determine the spectrum of antimicrobial resistance among bacteria identified in clinical specimens from Bangladeshi patients hospitalized with sepsis
  - Bacterial isolates from blood cultures will be identified, tested for antibiotic susceptibility. In a subset of antibiotic resistant isolates, genetic correlates of resistance will be assessed (A comprehensive microbiological analysis plan is provided in section 3.6).
- To compare the patient care costs between study arms
  - Direct medical costs of prescribed antibiotics, the PCT assay and hospital stay costs.

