### 2.2 Study design

#### Brief Description

##### Trial design

Randomised controlled, non-blinded, two-arm, parallel, clinical trial comparing Standard practice to procalcitonin guided de-escalation of antibiotic therapy.

---

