### 2.3 Determination of sample size

The sample size calculation is based on the expected difference in mean length of antibiotic treatment between the experimental and control arm. Based on retrospectively collected data from CMCH, the mean length of therapy (LOT) in sepsis patients was 5.2 days with a standard deviation (SD) of 8 days. The SD of the duration of antibiotic prescription in population level was derived by dividing the difference between the maximum and minimum value of LOT that was obtained from the retrospective data by four as one of the rules of thumb. The SD is assumed to be the same in the experimental and the control arms. We hypothesize to have a higher mean number of days of LOT in the control group as compared to the experimental group – i.e 5.2 days in the control group vs. 3.2 days in the experimental group, for an absolute reduction of mean LOT of 2 days. The level of significance was set at 5% (i.e., alpha=0.05). Based on these assumptions and estimating with 80% power, a total of 506 participants are required (i.e., 253 in the experimental arm and 253 in the control arm) to verify the study hypothesis. We anticipate a 5% loss to follow-up and to compensate for this, a total of 532 participants will be enrolled (266 in the experimental arm and 266 in the control arm). The sample size calculations have been performed in R software (version 4.2.1).

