**4.1 Guide to the calculation of the Length of Therapy (LOT), Days of Therapy (DOT) and the Defined Daily Dose (DDD)**
**Length of therapy (LOT) calculation.**

LOT is defined as the number of days of antibiotic treatment during the study period. Length of treatment will be measured from the day of enrolment to completion of the study follow up (28 days after hospital discharge). The primary outcome data for participants with recurrent infections will be censored at the time of recurrent infection diagnosis, i.e. the recurrent date will be used as the stop date in the calculation of LOT. If the recurrent infection occurs after the patient already stopped antibiotics for the initial presenting infection, the actual stop date of the last dose of antibiotics administered for the initial infection will be used in the LOT calculations and not the recurrent infection date.

The stop date for each antibiotic will be when the treating team discontinues it. In special circumstances, such as patients who left the hospital against medical advice or were transferred to another facility, the stop date will be recorded as the date they left or were transferred, as it was not feasible for the study team to track antibiotic data consistently in both arms beyond these points. If a patient developed an alternative diagnosis during the study that required an extended or modified antibiotic regimen, each case was reviewed individually by an investigator panel to determine the maximum antibiotic duration that could be included in the analysis.

**Scenario 1:** As an example, suppose patient A was admitted to the hospital on 02 February 24 at 10:00 AM due to a urinary tract infection. At 4:00 PM the same day, this patient was enrolled into the PROCALBAN study and was discharged from the hospital on 08 February 24 at 10:00 AM. This patient received intravenous ceftriaxone, 1 gram administered every 12 hourly from the date of enrolment and then upon discharge, this patient was prescribed oral cefuroxime, 500mg every 8 hours, for a duration of 7 days i.e. the actual stop date time for this oral cefuroxime will be subsequently recorded in the database by the end of follow-up for this patient. The calculation of LOT (the primary outcome) will proceed as follows:

1. Hospital stay duration during enrolment will be calculated as follows:
  - Enrollment: February 2nd, 4:00 PM
  - Discharge: February 8th, 10:00 AM
  - Hospital stay duration:

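### Table 2 counts recurrent infection only after antibiotic de-escalation, whereas the declared safety endpoint has no such condition and the intervention changes when de-escalation happens

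*SAP*

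**What the plan says.** Section 2.1.3 lists the safety endpoints as "Overall mortality, mortality-associated with recurrent infection, and non-lethal recurrent infections". Nothing there ties recurrence to the state of antibiotic treatment.

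Table 2 in section 3.3 has one recurrence row: "Recurrent infection confirmed or suspected after de-escalation of antibiotic". It is laid out as n (%) for procalcitonin, control and total, with a p value. Tables 3 to 6, the adverse event tables, have no recurrence row.

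Section 2.2 describes the trial as "comparing Standard practice to procalcitonin guided de-escalation of antibiotic therapy". Section 2.3 plans for the strategy to shorten treatment: "5.2 days in the control group vs. 3.2 days in the experimental group, for an absolute reduction of mean LOT of 2 days".

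Section 4.1 censors LOT at a recurrence, "i.e. the recurrent date will be used as the stop date in the calculation of LOT". It then sets apart one case, "If the recurrent infection occurs after the patient already stopped antibiotics for the initial presenting infection", for which the actual stop date is used instead.

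**The concern.** The row that will be tested is narrower than the endpoint it is meant to report. The condition that narrows it is also not neutral between arms. De-escalation is what the intervention acts on, so a count that begins there begins at a different time in each arm, for a reason caused by treatment. Events before that point can drop out, and the period in which they can drop out is expected to be longer in the arm with longer courses.

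The SAP's introduction rests the case for the strategy on a safe reduction in antibiotic use, and recurrence is one of the few outcomes that speak directly to that. A p value from this row would be read as a randomised safety comparison, which it would not be.

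**Working it through.** **1. The texts side by side.** The endpoint in section 2.1.3 covers all recurrences. The Table 2 row covers recurrences after de-escalation. Section 4.1 has two LOT rules: use the recurrence date, or, if antibiotics had already stopped, use the stop date. The first rule has work to do only if recurrence can occur while antibiotics continue. So the SAP expects events that alter the primary outcome but may not be counted in the safety row. The words 'may not' are needed because the SAP does not define de-escalation; its introduction speaks of stopping or reducing treatment.

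**2. The plan's own figure.** The SAP gives no figure for recurrence. Its LOT inputs do reproduce the sample size. With a difference of 2 days, SD 8, alpha 0.05 (two-sided assumed) and 80% power, n per arm = 2 × (1.96 + 0.842)² × 8² / 2² = 251.2, so 252. The t-test version gives 252.13, so 253 per arm and 506 in total, as stated in section 2.3. The mean LOTs of 5.2 and 3.2 days are used below.

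**3. Time at risk after stopping.** Follow-up ends 28 days after discharge, so time at risk = stay + 28 − LOT, taking de-escalation as the end of therapy. Stay, counted from enrolment, is assumed and equal in both arms.

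| Stay (days) | Control | Procalcitonin | Ratio |
|---|---|---|---|
| 3 | 25.8 | 27.8 | 1.08 |
| 5 | 27.8 | 29.8 | 1.07 |
| 7 | 29.8 | 31.8 | 1.07 |
| 10 | 32.8 | 34.8 | 1.06 |

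If the procalcitonin stay is also 2 days shorter, its window is (stay − 2) + 28 − 3.2 = stay + 22.8. The control window is stay + 28 − 5.2 = stay + 22.8. The lengths are then equal, but the procalcitonin window starts and ends 2 days earlier.

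**4. Share of recurrences counted.** Assume the same true risk in both arms, recurrences spread evenly over the first T days from enrolment, and only events after stopping counted. The share counted is (T − LOT)/T, so the arms differ by 2/T.

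| T (days, assumed) | Control | Procalcitonin | Ratio | An assumed true 10% risk appears as |
|---|---|---|---|---|
| 33 | 84% | 90% | 1.07 | 8.4% v 9.0% |
| 14 | 63% | 77% | 1.23 | 6.3% v 7.7% |
| 10 | 48% | 68% | 1.42 | 4.8% v 6.8% |
| 7 | 26% | 54% | 2.11 | 2.6% v 5.4% |

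This treats every patient as stopping at the arm mean. Section 2.3 took its SD of 8 as a quarter of the observed range, so that range was 4 × 8 = 32 days and some courses run well beyond 7 to 14 days. The short-T rows show how the distortion behaves and are not estimates.

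**5. Under the change.** If recurrences are counted from randomisation over the same period, equal true risk gives equal expected counts, a ratio of 1.00.

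**The case against.** The strongest reply is that this is one loosely worded label in a table shell. The section 3.3 heading and the Table 2 title both refer to recurrent infections without condition. The shell has an open row, and the protocol, not at hand, may define recurrence as something that follows the end of treatment. That is possible. But the row is the only place where the endpoint is laid out for testing, and a programmer who follows it would apply the condition.

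A reader might infer that control patients, who are not assigned to de-escalation, cannot have the event at all, so that a large part of the control count vanishes. The SAP does not support this. The row has a control column and a p value, so control events are expected. Nothing says that stopping or reducing antibiotics in a control patient is not de-escalation, and the document offers no figure for how many controls would be missed.

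A reader might also infer that the row must make procalcitonin look worse. With equal true risk the extra time at risk pushes that way. However, uncounted on-treatment events come out of both arms to unknown degrees, and a shorter stay can cancel the difference in window length, so the net direction is not settled.

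Other points on that side also stand. If de-escalation includes reducing treatment, some recurrences during continuing antibiotics would be counted. If recurrences are spread over 33 days, the distortion at an assumed 10% risk is 10% × 2/33 × 266 = about 1.6 events per arm of 266. Keeping all patients in the denominator is normal intention-to-treat practice and is not a fault. Table 3 would show some new on-treatment infections, such as catheter-associated urinary infection, although it does not replace a recurrence count.

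**Conclusion.** The mismatch holds on the SAP's text alone: an unconditional endpoint in section 2.1.3, a conditional row in Table 2, and LOT rules in section 4.1 that expect the events the row can omit. Because the condition is a post-randomisation event whose timing the intervention changes, the row is not a clean randomised comparison of recurrence.

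The size is modest unless recurrences come early. Time at risk after stopping is about 6-8% longer in the procalcitonin arm with equal stays of 3 to 10 days, and equal in length if the procalcitonin stay is 2 days shorter. The effect grows if recurrences cluster soon after enrolment. Stay, recurrence risk and timing are assumptions; only the mean LOTs come from the SAP. The primary outcome is not affected. The change should still be made, because it is cheap and concerns a named safety endpoint.

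**What to change.** Reword the Table 2 row to recurrent infection from randomisation to the end of follow-up, whether or not antibiotics had been de-escalated or stopped, defined identically in both arms, with all randomised patients as denominator. State that denominator explicitly, since section 3.4 describes the safety set as enrolled patients who received antibiotics. Keep recurrence after antibiotic stop as a descriptive row without a p value. Showing confirmed and suspected cases separately is an optional addition, useful because staff know the allocation.

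The cost is wording and one table row; recurrence dates are already needed for LOT. The small downside is that recurrences during treatment must be told apart from failure of the initial infection to resolve, by a rule applied in the same way to both arms. One limit remains: the end of follow-up is tied to discharge, so total observation can still differ if stay differs (for example 7 + 28 = 35 against 5 + 28 = 33 days). The report should note this.

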**Handling of missing data**

Data validation rules will include range checks on numeric variables, skip-logic for conditional questions and consistency checks between related variables. Stringent checks will be performed for datapoints that are critical for the primary and secondary study outcome measures.

**3.4. Safety and tolerability of procalcitonin-guided de-escalation of antimicrobials**

The safety and tolerability outcome measures are assessed based on the occurrence of adverse events (AEs) and serious adverse events (SAEs) in the study arms. AEs will be summarised as shown in **Table 3** and **Table 5**. Adverse events (AEs) defined in the study protocol and occurring among participants during

## STATISTICAL ANALYSIS PLAN

the study will be graded according to CTCAE Version 5 and presented for comparison across both study arms.

Safety analyses will be performed on all enrolled patients who received antibiotics. Safety and tolerability of the procalcitonin arm versus control arm will be assessed by comparing the frequency (as %) of AEs and SAEs, using the Fisher's exact test or Chi-square test, as appropriate. Safety data will be presented in tabular and/or graphical format and summarised descriptively. Patients safety data will be analysed following the intention to treat analysis. All adverse event summaries will refer to adverse events related to antibiotic treatment, i.e. adverse events that developed or increased in intensity after antibiotic administration, such as hospital acquired fungal infections. AEs will be graded according to Common Terminology Criteria for Adverse Events (CTCAE) version 5.0. The relevant CTCAE table is appended to this document. The safety and tolerability summaries will be presented as shown in **Table 3 and Table 5**.

The 95% confidence intervals will be reported for proportions. The proportions will be compared between intervention and control groups. The analyses will be summarised in **Table 3 and Table 5**.

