## 2. Introduction and study summary

Antimicrobial resistance (AMR) is a global problem, resulting in increased morbidity and mortality from multidrug resistant bacterial infections that are challenging to treat. Low- and middle-income countries (LMICs), like Bangladesh, are disproportionately affected by AMR. Excessive use of antibiotics both inside and outside the hospital is thought to be an important driver of AMR in Bangladesh and other LMICs. Several studies have shown that sequential assessment of serum procalcitonin (PCT) concentrations is an effective and safe strategy to shorten the duration of antibiotic therapy in critically ill patients. In this strategy, a decrease of procalcitonin below a certain threshold prompts the clinician to stop or reduce antibiotic treatment. However, these studies were conducted in high resource settings with standard laboratory PCT testing at considerable costs. We propose to evaluate the use of sequential serum PCT measurement to guide de-escalation of antibiotic therapy in a randomised clinical trial in patients with sepsis in a large tertiary referral hospital in Chattogram, Bangladesh, using low-cost point-of-care quantitative procalcitonin measurements. Main endpoint of the trial will be the difference in antibiotic therapy duration between the study groups. If this study shows that PCT guided de-escalation of antibiotics results in a safe reduction in antibiotic usage, this will be an important strategy to reduce the antibiotic burden in hospitals in Bangladesh and comparable resource-limited settings, as well as other consequences of prolonged antibiotic therapy, including increased costs, prolonged duration of intravenous lines and duration of stay, and microbiota changes.

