### 3.5. Relationship of AEs to procalcitonin arm versus control arm

**Table 4. AE relationship to study group**

Adverse events	Procalcitonin		Placebo		Total
Number of related AEs (Yes)	XXXX		XXXX		XXXX
Total number of events	XXXX		XXXX		XXXX
Symptoms, n/N (%)					
Septic thrombophlebitis	X/XX (X.X)	X/XX (X.X)	X/XX (X.X)	X/XX (X.X)	X/XX (X.X)

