**Table 5. Summary of severe adverse events by study group**

Severe adverse events	Procalcitonin		Control		Total
Number of participants	XXXX		XXXX		XXXX
Total number of events	XXXX		XXXX		XXXX
Grading of adverse events					
Events, n/N (%)					
Deaths related to the study intervention such as death directly related to the early stopping of antibiotics or complications of prolonged use of antibiotics	X/XX (X.X)	X/XX (X.X)	X/XX (X.X)	X/XX (X.X)	X/XX (X.X)

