**Table 6. SAE relationship to study group**

Severe adverse events	Procalcitonin		Control		Total
Number of participants	XXXX		XXXX		XXXX
Total number of events	XXXX		XXXX		XXXX
Grading of adverse events					
Events, n/N (%)					
Deaths (related to intervention)	X/XX (X.X)	X/XX (X.X)	X/XX (X.X)	X/XX (X.X)	X/XX (X.X)

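### The declared safety endpoints get counts and a P value but no between-arm confidence interval, and the SAE summary table names only deaths attributed to the intervention

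*SAP*

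**What the plan says.** Section 2 of the SAP ties the value of the strategy to safety as well as to antibiotic use: "If this study shows that PCT guided de-escalation of antibiotics results in a safe reduction in antibiotic usage", it will matter for hospitals of this kind. Section 2.1.3 then declares three safety endpoints: death from any cause, death linked to a recurrent infection, and recurrence that is not fatal.

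Table 2 (section 3.3) has one all-cause mortality row and one row for recurrent infection of any outcome, each with n (%) by arm and a P value. An unnamed placeholder row follows.

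Section 3.4 bases safety and tolerability on "adverse events (AEs) and serious adverse events (SAEs) in the study arms", compared by chi-square or Fisher's exact test. On precision it says "The 95% confidence intervals will be reported for proportions" and places those analyses in Tables 3 and 5. Table 5 is titled "Summary of severe adverse events by study group", and its only named event is "Deaths related to the study intervention such as death directly related to the early stopping of antibiotics or complications of prolonged use of antibiotics". Table 6, the relationship table, also names only attributed deaths. On scope, section 3.4 says that "adverse event summaries will refer to adverse events related to antibiotic treatment, i.e. adverse events that developed or increased in intensity after antibiotic administration". Section 2.2 states that staff and patients know the allocation.

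**The concern.** The efficacy claim and the safety claim need different things from the analysis. A test that rejects equality supports a claim that antibiotic days fell. A claim that the reduction was safe will most likely rest on finding no clear difference in deaths or recurrences, and a non-significant P value does not support that by itself. The reader needs to know how large an excess the data still allow, and that is the limit of the between-arm interval. As drafted, the tables do not give it for any of the three endpoints.

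The second part concerns the SAE display. A summary table should show what happened in each randomised arm, and a relationship table should show what was judged to be caused by the intervention. Here both name the same kind of event, deaths attributed with the arm known. Non-fatal SAEs have no named place, and all-cause death does not appear in the SAE summary.

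**Working it through.** **The plan's own figure.** Section 2.3 uses a 2-day difference, SD 8, 5% alpha and 80% power. The normal formula gives 2 × (8 × (1.960 + 0.842) / 2)² = 251.2, so 252 per arm. The t-test solution is 252.13, rounded up to 253 per arm or 506 in total, as stated. Adding 5% gives 506 × 1.05 = 531.3, so 532, or 266 per arm. The sample size reproduces and is not in dispute. It was set for length of therapy, not for safety.

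**Endpoints against table rows.**

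| Declared safety endpoint (2.1.3) | Row in Table 2 | Between-arm interval |
|---|---|---|
| All-cause mortality | yes | none stated |
| Recurrence-associated mortality | none named | none stated |
| Non-lethal recurrence | only within the pooled recurrence row | none stated |

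**Precision of a difference.** The SAP gives no event rate, so the rates below are assumptions. With equal true risk p and 266 per arm, the half-width is 1.96 × √(2p(1 − p)/266):
- p = 0.10: 1.96 × √(0.18/266) = 5.1 points
- p = 0.20: 1.96 × √(0.32/266) = 6.8 points
- p = 0.30: 1.96 × √(0.42/266) = 7.8 points
- p = 0.05 (for recurrence): 1.96 × √(0.095/266) = 3.7 points

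With 253 per arm, the mortality figures become 5.2, 7.0 and 8.0 points.

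**Chance that a real excess is non-significant.** Power for a true 5-point rise is Φ((0.05 − 1.96·SE₀)/SE₁), where SE₀ is pooled and SE₁ unpooled. For 20% against 25%, SE₀ = √(0.225 × 0.775 × 2/266) = 0.0362 and SE₁ = √((0.16 + 0.1875)/266) = 0.0361, so power is Φ(−0.58) = 28%. From 10% it is 41%, and from 30% it is 23%. A true 5-point excess would more often than not give P > 0.05.

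**What the reader would see.** Suppose 72 deaths against 53 (procalcitonin against control):
- Risks: 72/266 = 27.1% and 53/266 = 19.9%; difference 7.1 points.
- SE = √(0.2707 × 0.7293/266 + 0.1992 × 0.8008/266) = 0.0366; 95% CI −0.04 to 14.3 points.
- Chi-square P = 0.052 (Fisher 0.065).

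Table 2 would print 72 (27.1), 53 (19.9) and 0.052. The 14.3-point upper limit would not appear. Arm-level intervals (21.7% to 32.4% and 15.1% to 24.7%) would not give it either. This example was chosen to lie near P = 0.05. The half-widths above do not depend on that choice: with 53 deaths in each arm, the interval is still about ±6.8 points.

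**SAE shells.** Tables 3 and 4 carry a row for other events. Tables 5 and 6 have neither such a row nor a placeholder, only counts of participants and of total events above the single attributed-death row. Section 3.4 speaks of *serious* events and the table headings of *severe* ones, so the shell does not show which events the total counts.

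**The case against.** *A reader might infer that adverse events will be filtered by unblinded causality judgements, to the advantage of the procalcitonin arm.* The document does not support this. Section 3.4 defines *related* by timing, and Table 4 sets related events beside total events, which would serve little purpose if every summary were already filtered by causality. No direction follows from the death row either, since it covers deaths from early stopping as well as deaths from prolonged treatment. What remains is a loose word.

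*A reader might infer that deaths could go unreported.* They could not. Table 2 gives all-cause mortality by arm without attribution, together with organ-dysfunction items such as ventilation and shock. The gap is in the SAE summary and in non-fatal SAEs.

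*The missing interval is only shell detail.* Part of this stands. Table 2 gives no between-arm interval for length of therapy either, nothing in the SAP rules one out, and anyone can compute one from the counts. The plan also sets no safety hypothesis or margin, and none is asked for here. But leaving the calculation to readers means that the analysis behind the safety conclusion is not fixed in advance.

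*The open row could hold the missing endpoint, and SAE scope may be set in the protocol.* Both are possible. The open row names nothing, however, and a protocol definition would not alter a summary table whose only named event is an attributed death.

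**Conclusion.** The point holds as a reporting weakness that is worth correcting before analysis. No between-arm interval is stated for mortality or recurrence, one declared safety endpoint has no named row, and another is not separated from a pooled row. At 266 per arm, and on assumed mortality of 10% to 30%, the unreported uncertainty is about ±5.1 to ±7.8 points; at an assumed 5% recurrence it is about ±3.7 points. These sizes rest on assumed rates, equal true risks and complete data, and would be slightly larger with 253 per arm. The SAE summary names only attributed deaths in an open-label trial, while all-cause mortality is secure in Table 2. The primary analysis is not affected. No bias, and no direction of bias, is claimed for the adverse-event wording.

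**What to change.** 1. In section 3.3 and Table 2, report the risk difference with its 95% CI for all-cause mortality, recurrence-associated mortality and non-lethal recurrence, and give the last two their own rows.
2. In Table 5, list all-cause deaths and all SAEs that the protocol collects, by randomised arm and regardless of attribution. Leave relatedness to Table 6.
3. Wording only: use one term, *serious* or *severe*, for SAEs in section 3.4 and in Tables 5 and 6, and drop *related to* from the adverse-event sentence so that the timing definition stands alone.

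The change is to SAP text and table shells. It needs no new data beyond what the protocol already collects and no change to the sample size. The price is longer tables.
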